9.7.2 Biomarker assessments in blood samples

Biomarker assessments will also be performed using whole blood samples to investigate potential pharmacodynamic markers and explore the relationship to efficacy and/or mechanism of action of GEN1029. Assessments will be performed at baseline (before infusion at C1D1) and at later cycles during treatment including visits in close proximity with a planned CT scan, and at the end of treatment in order to enable correlation analyses with response to treatment or disease progression.

Protein expression analyses

Levels of proteins related to GEN1029's mechanism of action, including levels and activation status of complement components and cytokines, may be measured so changes associated with the mechanism of action of GEN1029 can be monitored.

Immunophenotyping analyses

Immunophenotyping, including single cell sorting/sequencing, may be performed (for example; measurement of ______) at baseline and during treatment so changes associated with the mechanism of action of GEN1029 can be monitored.

9.7.3 Additional analyses

In addition to the biomarker analyses listed above, other biomarkers deemed relevant to gain further knowledge about the pathomechanism of the disease or about GEN1029 (i.e. mode of action related effect or safety of the drug) may be measured, based on newly emerging data from other ongoing trials and/or literature data. Biomarker samples may further be used to help address emerging issues and to enable the development of safer, more effective, and, ultimately, individualized therapy.

Genmab

Moreover, biomarker analyses are dependent upon the availability of appropriate biomarker assays and clinical response rates. Biomarker analysis may be deferred or not performed, if during or at the end of the trial, it becomes clear that the analysis will not have sufficient scientific value for biomarker evaluation, or if there are not enough samples or responders to allow for adequate biomarker evaluation. In the event the trial is terminated early or shows poor clinical efficacy, completion of biomarker assessments is based on justification and intended utility of the data.

10 SAFETY MONITORING AND ADVERSE EVENT REPORTING

10.1 Adverse Event Definitions

10.1.1 Definition of Adverse Event

An adverse event (AE) is any untoward medical occurrence in a patient or clinical trial patient, temporally associated with the use of a medicinal product, whether or not considered related to the medicinal product. An AE can therefore be any unfavorable and unintended sign (including an abnormal laboratory finding), symptom, or disease (new or exacerbated) temporally associated with the use of a medicinal product.

AEs (including laboratory abnormalities that constitute AEs) should be described using a diagnosis whenever possible, rather than individual underlying signs and symptoms. When a clear diagnosis cannot be identified, each sign or symptom should be reported as a separate AE.

10.1.2 Definition of Serious Adverse Event

A serious adverse event (SAE) is defined as an adverse event that meets one of the following criteria:

- Is fatal or life-threatening¹
- Results in persistent or significant disability/incapacity
- Constitutes a congenital anomaly/birth defect
- Is medically significant, i.e., defined as an event that jeopardizes the patient or may require medical or surgical intervention to prevent one of the outcomes listed above. Medical and scientific judgment must be exercised in deciding whether an AE is "medically important"
- Requires inpatient hospitalization or prolongation of existing hospitalization²

¹ The term "life-threatening" in the definition of "serious" refers to an event in which the patient was at risk of death at the time of the event; it does not refer to an event which hypothetically might have caused death if it was more severe.

² Hospitalizations for the following reasons should not be reported as SAEs:

- Routine treatment or monitoring of the studied indication, not associated with any deterioration in condition
- Elective or pre-planned treatment for a pre-existing condition during trial that has not worsened since signing the informed consent
- Social reasons and respite care in the absence of any deterioration in the patient's general condition
- Treatment on an emergency outpatient basis that does not result in hospital admission and involves an event not fulfilling any of the definitions of a SAE given above

10.1.3 Definition of Adverse Events of Special Interest (AESI)

Adverse events of special interest (AESI) are defined as events (serious or non-serious) which are of scientific and medical concern specific to the sponsor's product or program, for which ongoing monitoring and rapid communication by the investigator to the sponsor may be appropriate. Such events may require further investigation in order to characterize and understand them.

Adverse events of special interest are defined on the basis of an ongoing review of the safety data. AESIs are discussed further in Section 10.3 and in the investigator's brochure.

10.1.4 Definition of Infusion-Related Reactions

Infusion-related AEs are defined as any AEs occurring during infusion or where the onset of the event occurs within 24 hours after the end of infusion and is coded by Medical Dictionary for Regulatory Activities (MedDRA) preferred term as:

"Arthralgia", "Asthenia", "Bronchospasm", "Chills", "Cough", "Hyperhidrosis", "Dizziness", "Pyrexia", "Fatigue", "Flushing", "Headache", "Hypertension", "Hypotension", "Infusion related reaction", "Lethargy", "Malaise", "Myalgia", "Nausea", "Pruritus", "Tachycardia", "Tumor pain", or by MedDRA High Level term as "Exfoliative conditions" or "Dyspneas", "Dyspneas", "Breathing abnormalities" or by MedDRA High Level Group Term as "Allergic conditions".

Investigators should consider the clinical picture and isolated events, such as "Fatigue", occurring within 24 hours after the end of infusion, might be considered not to constitute an infusion-related reaction, if judged not to be infusion-related by the investigator.

For infusion-related reactions the causality of the event (Section 10.2.11) should be judged as "at least possibly related" by the investigator.

10.2 Adverse Event Reporting

Non-serious Adverse Events:

Non-serious AEs should be reported from the time the patient signs the ICF until the safety follow up visit (at 70 days after the last IMP dose) or the end of trial (EOT)/withdrawal visit), whichever comes first.

Serious Adverse Events

SAEs should be reported from the time the patient signs the ICF until the safety follow up visit (at 70 days after the last IMP dose) or the end of trial (EOT)/withdrawal visit, whichever comes first.

Please note:

- Final assessment of AEs must be performed by a medically qualified person, i.e., a medical doctor.
- All AEs that occur in patients during the AE reporting period must be reported, whether or not the event is treatment-related.
- All AEs should be entered in the eCRF and assessment should be made at each visit (or more frequently, if necessary) of changes in severity, the suspected relationship to the trial treatment, action taken to trial drug, and the outcome. Instructions for reporting changes in an ongoing AE during a patient's participation in the trial are provided in the eCRF completion guideline.
- If an AE becomes grade 3 or results in an SAE it should be reported both in the eCRF and on the relevant paper form (SAE paper form or non-serious grade 3 form).
- All AEs should be followed until they are resolved or until end of trial, whichever comes first. At least possibly related non-serious ≥ grade 3 AEs and SAEs still ongoing after end of trial should be followed on a regular basis, according to the investigator's clinical judgment, until the event has been resolved or until the investigator assesses it as chronic and all queries have been resolved.

10.2.1 Pre-existing Condition

In this trial, a pre-existing condition (i.e. a disorder present before the AE reporting period started and noted on the medical history/physical examination form) is not to be reported as an AE. If a pre-existing condition worsens during the IMP treatment period, the event should be reported as an AE.

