4 TRIAL DESIGN

4.1 Description of Trial Design

This is an open-label, multi-center phase I/IIa safety trial of GEN1029 in a mixed population of patients with solid tumor types. The trial consists of two parts; a dose escalation part (phase I, FIH) and an expansion part (phase IIa) as depicted in Figure 4-1.

Figure 4-1

In the dose escalation part, up to 2 dose regimens may be evaluated; these are described in Section 4.2. Those dose regimens, that are considered to be safe by the Data Monitoring Committee (DMC) and the sponsor safety committee, and for which a recommended phase 2 dose (RP2D) is established, may be further explored in the expansion part. Each expansion cohort will only include patients with one selected indication who are to be treated with one selected dose regimen. More than one dose regimen may be evaluated per indication, but in different cohorts.

Patients in both parts of the trial will receive treatment until disease progression. Thus, the treatment period will last until unacceptable toxicity or disease progression is observed. Efficacy will be assessed every six weeks primarily based on CT-scans. The RECIST 1.1 criteria will be used for response evaluation (Eisenhauer et al., 2009).

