4.8.2 End of Treatment

For each patient the treatment period will be until progression (cycles of 14 days) unless the patient fulfills one of the discontinuation of treatment criteria (see Section 8.1).

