11.4.1.1 Primary Endpoints

- Number of DLTs during the DLT period (initial 28 days of treatment). See Section 4.3 for how the MTD will be determined.
- Summary tables for adverse events (AEs) will include only AEs that started or worsened during the on-treatment period, the treatment-emergent AEs.

The incidence of treatment-emergent adverse events (new or worsening from baseline) will be summarized by System Organ Class (SOC) and or Preferred Term (PT), severity (CTCAE grade), type of adverse event, and relationship to IMP.

SAEs, non-serious AEs and AEs of special interest (AESI) during the on-treatment period will be tabulated.

All deaths (on-treatment and post-treatment) will be summarized.

All AEs, deaths and SAEs (including those from the pre and post-treatment periods) will be listed and those collected during the pre-treatment and post-treatment period will be flagged.

Further summaries of AEs will be specified in the statistical analysis plan.

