#### 4.1 Trial Period and Visit Window Definitions

#### 4.1.1 Trial Periods

Screening period will be defined as the period between signature of the ICF and the date of first IMP administration.

On-Treatment period will be defined as the period between first IMP administration (included) and last IMP administration, including the safety follow-up period (taking the maximum of date of last IMP +70 days, end of treatment visit and safety FU visit).

Follow-up period will be defined as the period after the On-Treatment period (that includes the safety FU period) +1 day until the date of last contact.

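### Protocol 10.2.1 ties reporting of a worsened pre-existing condition to an undefined treatment period that may end 57 to 70 days before the TEAE window closes, so the TEAE tables may undercount such worsening

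*Protocol*

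**What the plan says.** Protocol 10.2.1 deals with disorders that were present before AE reporting began and are noted on the medical history or physical examination form. Such a condition "is not to be reported as an AE". If it worsens "during the IMP treatment period, the event should be reported as an AE". The length of that period is not defined.

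Elsewhere the protocol describes the treatment period without any follow-up. In 4.1, "the treatment period will last until unacceptable toxicity or disease progression is observed"; 4.8.2 likewise runs it to progression unless the patient discontinues earlier. Section 8.3 places the 30- and 70-day safety visits after discontinuation of treatment.

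The AE rules use a longer window. Section 10.1.1 counts an exacerbated disease as an AE. Section 10.2 runs reporting from consent to the visit 70 days after the last dose, or to the end-of-trial or withdrawal visit if that comes first, and adds: "All AEs that occur in patients during the AE reporting period must be reported, whether or not the event is treatment-related".

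On the analysis side, Protocol 11.4.1.1 says: "Summary tables for adverse events (AEs) will include only AEs that started or worsened during the on-treatment period". SAP 4.1.1 extends that on-treatment period through safety follow-up, "taking the maximum of date of last IMP +70 days, end of treatment visit and safety FU visit". SAP 17.3 applies the same started-or-worsened rule and uses the dates of grade changes.

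**The concern.** The instruction that governs what a site enters and the window over which the tables claim to count worsening do not match. A medical-history condition that is never entered as an AE cannot appear in a TEAE table, whatever the SAP says about worsening. New-onset events in the same follow-up days would be entered.

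This matters because AEs are listed as a primary endpoint in Protocol Table 3-1 and 11.4.1.1, and because patients may enter with conditions that can worsen. Exclusion criterion 11 tolerates chronic fatigue or anorexia up to grade 2 from earlier therapy. The inclusion criteria admit ALT/AST up to 3 times ULN and hemoglobin of about 9 g/dL. A patient with a DLT must stop drug at once (7.1), so patients who stop early spend most of their observed time in follow-up. If some sites follow 10.2.1 and others 10.1.1, ascertainment also differs between sites.

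**Working it through.** The plan gives no figure on this point to reproduce. The check sets the windows side by side and counts days after the last dose (day 0 = last dose).

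**Inputs**
- Worsening rule, Protocol 10.2.1: ends with the IMP treatment period, undefined. Let *e* be its last day.
- AE reporting, Protocol 10.2: ends at the 70-day visit, or at end of trial/withdrawal if earlier.
- TEAE window, SAP 4.1.1 and 17.3: ends at day 70 or later.
- Candidate values for *e*: 0 (treatment ends with the last dose); 13 (SAP 4.6 takes last IMP + 13 as the end of IMP when computing treatment duration for the biweekly and priming regimens, unless last contact or cut-off is earlier); 70 (the term is read as the SAP's on-treatment period).

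**Gap before day 70 = 70 − *e***

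| Reading of the treatment period | Days not covered by 10.2.1 |
|---|---|
| Ends at last dose | 70 − 0 = 70 (days 1 to 70) |
| Ends at last dose + 13 | 70 − 13 = 57 (days 14 to 70) |
| Equals the SAP on-treatment period | 70 − 70 = 0 |
| 10.2.1 referred to the AE reporting period | 0 up to the 70-day visit |

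The 57 and 70 are upper limits for an individual patient. Reporting under 10.2 stops earlier if the patient leaves the trial. In dose escalation, which is the only part that was run (SAP 3), starting another anti-cancer treatment is itself a reason for withdrawal (Protocol 8.2).

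**Which kinds of worsening could be lost**
- *Laboratory.* Protocol Table 1-1 schedules hematology and biochemistry at both safety visits. SAP 17.5 tabulates the highest on-treatment grade, shifts from baseline to worst grade using scheduled and unscheduled values, liver threshold categories and grade 3 or 4 results. None of these needs an AE entry.
- *Non-laboratory.* Table 1-1 schedules no body weight, physical examination or ECOG assessment at the 30- and 70-day visits. Worsening of fatigue or anorexia at that stage depends on an AE entry.
- *DLT.* The DLT period is the first 28 days (SAP 3.2), and a patient who stopped drug for a DLT is already counted.

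The same wording leaves out worsening between consent and first dose, although AE reporting starts at consent. That does not touch the TEAE tables.

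**The case against.** The best case on the other side is that nothing is actually excluded. Section 10.2.1 does not say that later worsening is not an AE. Section 10.1.1 covers exacerbation, 10.2 makes reporting of all AEs mandatory to the 70-day visit, and Table 1-1 schedules AE collection at both safety visits. If the undefined term is taken to mean the SAP's on-treatment period, the gap is zero. Deaths and Hy's law cases must be reported as SAEs in any event (10.2.4, 10.4.1), and a DLT is already in the database and is followed as an AE.

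Much of this stands. A reader might infer that worsening after treatment is definitely missing from the primary safety tables. The documents do not support that, because two general rules point towards reporting. Nor is the SAP's TEAE definition at fault: it excludes nothing here, and any loss would arise at the site. A reader might also turn days into events, noting that after a single dose 57 of the 71 days from day 0 to day 70 (57/71 = 80%) are uncovered if the period ends at day 13. That is a share of calendar time under one reading, with full follow-up assumed. It is not a share of events.

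What does not stand is that the general rules settle the matter. Section 10.2.1 is the specific instruction for this case, and a site applying it as written would record nothing. Investigators report from the protocol, and nothing in the protocol equates the two terms.

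**Conclusion.** This is an internal inconsistency that may lead to under-recording. It is not a proven exclusion. Read literally, the site rule for worsening stops up to 57 days (period ends at last IMP + 13) or up to 70 days (period ends at last dose) before day 70 of the TEAE window. The likely effect is an undercount of non-laboratory worsening of baseline conditions, and uneven recording between sites.

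The conclusion rests on two assumptions: that at least some sites read the treatment period as 4.1 and 4.8.2 use it, and that the eCRF completion guideline, which is not among the documents, does not already correct this. The number of affected events cannot be calculated. The SAP names only DLT as the primary endpoint (17.1), so the effect bears on the TEAE summaries that the protocol lists under primary endpoints and hardly on dose determination.

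**What to change.** In Protocol 10.2.1, replace the reference to the IMP treatment period with the AE reporting period of section 10.2, and align the eCRF completion guideline. Worsening is then collected from consent to the 70-day visit, in line with 10.1.1 and with the window in which the SAP tabulates it. If data collection is already complete, the trial report should state which rule sites applied, so that readers can judge the follow-up part of the TEAE tables.

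The cost is one phrase in the protocol, a matching line in the guideline and a few additional AE entries in follow-up. No visit, sample or analysis definition changes.

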10.2.2 Diagnosis

The diagnosis/cause of an AE should be recorded rather than the symptoms of the AE. If no diagnosis is available each sign and symptom should be recorded as individual AEs.

10.2.3 Study Disease

Signs and symptoms, which according to the investigator are expected and well known consequences of the indication, both in intensity and frequency, should not be reported as AEs or SAEs. Any unexpected change in the intensity or frequency should be reported as an AE (or SAE if applicable).

10.2.4 Disease Progression or Death

Progression of malignancy, if documented by use of an appropriate method (as per RECIST criteria), should not be reported as an SAE. However all deaths (including death caused by disease progression) should be reported as SAEs.

10.2.5 Unrelated Procedures

Diagnostic and therapeutic non-invasive and invasive procedures, such as surgery, should not be reported as AEs. A medical condition for which an unscheduled procedure was performed, should however be reported if it meets the definition of an AE. For example, an acute appendicitis should be reported as the AE and not the appendectomy.

10.2.6 Laboratory test abnormalities

Laboratory abnormalities that are considered clinically significant, i.e. induce clinical signs or symptoms, require concomitant therapy or require changes in trial treatment should be recorded as an AE in the eCRF. Whenever possible, a diagnosis, rather than a symptom should be provided (e.g. anemia instead of low hemoglobin). Laboratory abnormalities that meet the criteria for AEs should be followed until they have returned to normal or an adequate explanation of the abnormality is found. When an abnormal laboratory or test result corresponds to a sign/symptom of an already reported AE, it is not necessary to separately record the laboratory/test result as an additional event.

NOTE: A CTCAE grade 3 or 4 event (severe) does not automatically indicate an SAE.

10.2.7 Start Date and Time

Start date for an (S)AE is the date of occurrence of the first symptom of the disease, e.g. if chest pain occurs on 01 April 2016 and the patient is hospitalized with myocardial infarction on 04 April 2016, then the onset date of the SAE myocardial infarction is 01 April 2016.

The time should be filled in if the event starts on a dosing day or if the duration of the event is less than 24 hours.

If the start date of an AE is the same as an infusion date, the investigator is to assess whether the AE is related to the infusion.

10.2.9 Seriousness Criteria

Indicate whether or not the AE is determined to be "serious" based on the criteria defined in Section 10.1.2.

10.2.10 Intensity

The investigator will use the NCI's CTCAE version 4.03 to describe the severity of AEs.

10.2.11 Relationship to Investigational Medicinal Product

A suspected adverse reaction is one in which there is a reasonable possibility that the IMP caused the adverse event, this means there is evidence to suggest a causal relationship between the IMP and the adverse event.

The investigator must assess whether or not the event is related to the IMP. The relationship is to be judged using the following terms:

- At least possibly related
- Not related

If the relationship changes over time, the last judgment by the investigator should be reported. Relatedness has to be assessed and reported from the first time the AE is being reported.

10.2.12 Action Taken with Investigational Medicinal Product

The action taken with the IMP should be noted as:

- Dose not changed
- Dose reduced
- Drug interrupted
- Drug withdrawn
- Not applicable
- Unknown

Drug interrupted should be use if the infusion is interrupted or if a treatment is postponed due to mitigation of AEs.

Not applicable should only be used if the AE occurs before first treatment or in the follow-up period.

10.2.13 Outcome

The outcome of the AE must be judged by investigator using the following terms:

- Fatal
- Not recovered/not resolved
- Recovered/resolved

- Recovered/resolved with sequelae
- Unknown

10.2.14 End Date and Time

The end date should be filled in if the outcome of an event is fatal, recovered/resolved or recovered/resolved with sequelae. The time should be filled in if the event starts on a dosing day or if the duration of the event is less than 24 hours.

10.3 Adverse Events of Special Interest

10.3.1 Elevation of Transaminases

Alanine aminotransferase (ALT) increased and aspartate aminotransferase (AST) increased have been reported in more than 50% of the patients. The majority of these were considered to be related to the IMP and appeared to be independent of the dose level. Guidance for managing elevated transaminases has been included in Section 7.2.2.1.

10.3.2 Diarrhea

Diarrhea has been reported in more than 40% of the patients and was the most frequently reported SAE. The majority of these were considered to be related to the IMP. Guidance for managing diarrhea has been included in Section 7.2.2.3.

